#### **6.4.3.3 Pregnancy**

Pregnancy in a female subject who has received investigational product is required to be reported *within 24 hours of knowledge of the event* to MedImmune Patient Safety or designee using the Fax Notification Form (see Section 6.4.2.2 for contact information).

Subjects who become pregnant during the study period must not receive additional doses of investigational product and will be withdrawn from the study. After obtaining the subject's consent, the pregnancy will be followed for outcome of the mother and child (including any premature terminations) and should be reported to MedImmune Patient Safety or designee after outcome.

#### **6.4.3.4 Events Meeting Study Stopping Criteria**

Events that meet any of the study stopping criteria (see Section 3.3), with or without associated AEs or SAEs, are required to be reported within 24 hours of knowledge of the event to MedImmune Patient Safety using the Safety Fax Notification Form (see Section 6.4.2.2 for contact information). The occurrence of these events does not automatically make an AE serious, but if the consequences of the event are serious, for example death or hospitalization, the event is serious and must be reported as an SAE (see Section 6.3.1 and Section 6.4.2).

#### **6.4.4 Study Reporting Period for Other Events of Special Interest**

Any infusion reaction of a study subject with the investigational product causing permanent discontinuation of dosing with investigational product, with or without associated AEs/SAEs,

is required to be reported within 24 hours of knowledge of the event to MedImmune Patient Safety or designee using the Fax Notification Form (see Section 6.4.2.2 for contact information). An infusion reaction does not automatically make an AE serious, but if the consequences of the reaction are serious, for example death or hospitalization, the event is serious and must be reported as an SAE (see Section 6.3.1 and Section 6.4.2).

## **6.5 Safety Management During the Study**

The medical monitor has primary responsibility for the ongoing medical review of safety data throughout the study. This includes review of SAEs and timely review of AEs and “other events” reported during the study. MedImmune Patient Safety is responsible for the receipt, immediate medical/clinical review, investigation, and follow-up of SAEs and other immediately reportable events (eg, overdose, pregnancies, and infusion reactions) reported from the clinical study sites.

The MedImmune SMC, chaired by the MedImmune Chief Medical Officer, provides safety surveillance, guidance, and oversight for all clinical development studies in which MedImmune has sponsor accountabilities. In addition to the Chief Medical Officer, SMC members include the heads of Patient Safety, Clinical Development, and Regulatory Affairs, and external physician members with expertise in relevant therapeutic areas. The SMC reviews protocol-specific safety data at regularly scheduled meetings and ad hoc meetings, and provides oversight for individual study protocol safety committees. Based on review of safety data, the SMC may suspend enrollment or subject dosing in clinical studies, request modification of study documents, or take other actions as deemed necessary.

## **7 Statistical Considerations**

### **7.1 General Considerations**

Data will be provided in data listings sorted by SID. Tabular summaries will be presented such that categorical data will be summarized by the number and percentage of subjects in each category and continuous variables will be summarized by descriptive statistics, including mean, standard deviation, median, minimum, and maximum. Confidence intervals (CIs) will be 2-sided, unless otherwise stated. Details of endpoint analyses will be described in the Statistical Analysis Plan.

## 7.2 Analysis Populations

The intent-to treat (ITT) population will include all subjects entered into the study. The ITT population is the primary population for the efficacy analyses and the summary of baseline characteristics.

The evaluable population will include all subjects who received at least 1 dose of MEDI-575 and had at least 1 post-baseline disease assessment. The evaluable subject population will be the secondary population for efficacy analysis.

The safety population will include all subjects who receive at least 1 dose of MEDI-575 and will be used to summarize the safety assessments.

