### **5.2.4 Every 2 Cycles, Beginning with Cycle 3**

The following evaluations will be performed every 2 cycles (ie, every 6 weeks) unless otherwise indicated, beginning at Cycle 3 (eg, Cycle 3, Cycle 5, etc.)

- 1) Assess for disease response:
  - MRI scan (within 7 days prior to start of cycle)

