### **5.2.5 Treatment Discontinuation Visit**

The following evaluations will be performed at the time (or up to 5 days after) the subject completes therapy or is withdrawn/discontinued from the study therapy, or at the time of first objective disease progression, whichever comes first. Any procedures conducted within 14 days before treatment discontinuation (eg, procedures conducted on Day 1 of a cycle) do not need to be repeated at the treatment discontinuation visit.

- 1) Perform complete physical examination (if applicable, record new findings as AEs or SAEs)
- 2) Assess for AEs and SAEs
- 3) Update concomitant medications
- 4) Obtain vital signs (temperature, blood pressure, pulse, respiratory rate) including weight (-1 day allowed for weight)
- 5) Assess ECOG performance status
- 6) Collect blood samples for:
  - Serum chemistry (-1 day allowed)
  - Hematology (-1 day allowed)
  - Coagulation parameters (-1 day allowed)
  - Anti-MEDI-575 antibodies
  - MEDI-575 serum concentration
  - Circulating soluble proteins
  - Circulating apoptotic markers
  - Circulating mRNA/miRNA
- 7) Collect urine for routine urinalysis (-1 day allowed)
- 8) Perform 12-lead ECG

- 9) Obtain consent and collect fresh tissue tumor biopsy (optional)
- 10) Administer PRO questionnaires (-3 days allowed)
  - EORTC QLQ-C30
  - EORTC QLQ-BN20
- 11) Disease evaluations:
  - MRI scan

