- Progression-free survival will be measured from the start of treatment with MEDI-575 until the documentation of disease progression or death due to any cause, whichever occurs first. Progression-free survival will be censored on the date of last tumor assessment documenting absence of tumor progression for subjects who have no documented progression and are still alive prior to data cutoff, dropout, or the initiation of alternate anticancer treatment. Subjects having no tumor assessments after the start of treatment with MEDI-575 will have PFS censored on the first date of treatment with MEDI-575. Progression-free survival will be evaluated using the Kaplan-Meier method.
- Overall survival will be determined as the time from the start of treatment with MEDI-575 until death. For subjects who are alive at the end of study or lost to follow-up, OS will be censored on the last date when subjects are known to be alive. Overall survival will be evaluated using the Kaplan-Meier method.

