Progression	
Defined by any of the following: <math>\geq 25\%</math> increase in sum of the products of perpendicular diameters of enhancing lesions compared with the smallest tumor measurement obtained either at baseline (if no decrease) or best response, on stable or increasing doses of corticosteroids*; significant increase in T2/FLAIR nonenhancing lesion on stable or increasing doses of corticosteroids compared with baseline scan or best response after initiation of therapy* not caused by comorbid events (eg, radiation therapy, demyelination, ischemic injury, infection, seizures, postoperative changes, or other treatment effects); any new lesion; clear clinical deterioration not attributable to other causes apart from the tumor (eg, seizures, medication adverse effects, complications of therapy, cerebrovascular events, infection, and so on) or changes in corticosteroid dose; failure to return for evaluation as a result of death or deteriorating condition; or clear progression of nonmeasurable disease.

Note: All measurable and nonmeasurable lesions must be assessed using the same techniques as at baseline.

Abbreviations: MRI, magnetic resonance imaging; FLAIR, fluid-attenuated inversion recovery.

\*

Stable doses of corticosteroids include patients not on corticosteroids.

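### The evaluable population is selected on having a post-baseline assessment, so it drops early deaths and early failures and flatters OS and ORR in the secondary efficacy analysis

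*Protocol*

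**What the plan says.** Section 7.2 defines three populations. On the primary one it says: "The ITT population is the primary population for the efficacy analyses and the summary of baseline characteristics". The second is defined thus: "The evaluable population will include all subjects who received at least 1 dose of MEDI-575 and had at least 1 post-baseline disease assessment". Its role is also fixed: "The evaluable subject population will be the secondary population for efficacy analysis". No endpoint is exempted, and Sections 5.1 and 7.3.2.1 both list OS among the efficacy measures.

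Other parts of the protocol bear on who gets in:

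- Section 5.2.4 places the first on-treatment MRI in the week before Cycle 3.
- Section 5.2.5 adds an MRI when "the subject completes therapy or is withdrawn/discontinued from the study therapy", or at first objective progression if that comes sooner.
- Section 7.3.2.1 starts the survival clock at first dose: "Overall survival will be determined as the time from the start of treatment with MEDI-575 until death".
- The same section says of unscanned subjects: "Subjects having no tumor assessments after the start of treatment with MEDI-575 will have PFS censored on the first date of treatment with MEDI-575". It states no exception for those who died.
- Appendix 4 lists among the definitions of progression: "failure to return for evaluation as a result of death or deteriorating condition".

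**The concern.** Entry to the evaluable set depends on something that happens after treatment begins, and failing to reach it is often the outcome itself. A subject who dies in week 4 without a scan is a treated subject with a known result, yet is left out.

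For OS this is immortal time. Unless a discontinuation or unscheduled scan came first, nobody in the set can have died before the first scan. No scan is needed to observe a death, and Section 5.2.6.3 requires survival status from every subject. For ORR, people known not to have responded leave the denominator. The rule also conflicts with Appendix 4, which would call the same people progressors.

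With no control arm, the absolute rates are the result, and no comparator shares the bias.

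**Working it through.** **1. The plan's own figures.** The protocol gives no figure for the evaluable set. Its power statement can be reproduced, so the planning inputs are not in question: Φ[(0.30 − 0.16 − 1.645·√(0.16·0.84/50)) / √(0.30·0.70/50)] = Φ(0.0547/0.0648) = 80.1%, against 80% stated in Section 7.5.

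**2. Length of the window.** Day 1 is the first dose (Section 4.5.4) and cycles last 21 days. Cycle 3 Day 1 is then Day 43 and the scan window is Day 36 to 43, or 35 to 42 days after first dose if no cycle is delayed.

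**3. Which endpoints move.** Let d be the share of treated subjects removed.

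- *ORR* = responders / subjects. Unscanned subjects cannot be responders, so the evaluable rate is the all-treated rate × 1/(1 − d).
- *OS at a fixed time* becomes S(t)/(1 − d), provided everyone removed has died by t.
- *TTR and DR* are assessed only in responders, all of whom have assessments, so they do not change.
- *TTP* is censored at first dose for unscanned subjects. In the Kaplan-Meier product Π(1 − events/at risk), a subject censored at time zero is in no later risk set, so removal changes nothing.
- *PFS and PFS-6*, with the censoring sentence read literally, behave like TTP: among treated subjects the curve is the same with or without the unscanned. They differ only if an unscanned death counts as an event, as the any-cause-death wording in the PFS definition suggests.

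**4. Size for ORR.** d is not in the protocol; 2% to 10% is an assumed range.

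| d | 1/(1 − d) |
|---|---|
| 2% | 1.02 |
| 5% | 1.05 |
| 10% | 1.11 |

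For illustration, with 5 responders assumed: 5/55 = 9.1%; after 6 removals, 5/49 = 10.2%.

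**5. Size for OS, if all those removed are early deaths.** Section 1.4 cites a median OS of about 7 months on standard therapies; exponential survival is assumed.

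- S(6 months) = 2^(−6/7) = 55.2%.
- Deaths by 35 days (1.150 months): 1 − 2^(−1.150/7) = 10.8%. By 42 days (1.380 months): 1 − 2^(−1.380/7) = 12.8%.
- Median OS in the set = −ln[0.5(1 − d)]·7/ln 2.

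| d | 6-month OS | Median OS (months) |
|---|---|---|
| 0 | 55.2% | 7.0 |
| 5% | 0.552/0.95 = 58.1% | 7.5 |
| 10% | 0.552/0.90 = 61.3% | 8.1 |
| 12.8% | 0.552/0.872 = 63.3% | 8.4 |

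Under these assumptions, with cycles on schedule, the last row is an upper bound: it treats every death before Day 43 as unscanned.

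**6. PFS-6, only if unscanned deaths are events.** A true 30% would read 0.30/0.98 = 30.6%, 0.30/0.95 = 31.6% and 0.30/0.90 = 33.3%. Under the literal censoring sentence the extra inflation over ITT is zero.

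**The case against.** The best case on the other side has four parts.

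*ITT is primary.* This stands. A reader might infer that the trial's success call is exposed, because removing one failure can move a borderline result: 14/55 has a plain 90% lower bound of 15.8%, and 14/54 has 16.1%, against the 16% threshold. The protocol does not support that inference. Section 7.2 makes ITT primary and no decision rule is attached to the evaluable set. The shift also needs unscanned deaths to count as events and depends on the interval method, since the log-log bound for 14/55 is already 16.4%.

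*PFS is not inflated by this rule.* This largely stands. A reader might infer that every efficacy figure in the set is biased, PFS-6 included. As shown above, TTR, DR and TTP do not move, and with the censoring sentence taken literally neither does PFS. Any PFS bias on that reading comes from the censoring sentence and is shared with ITT.

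*The number removed may be small.* This stands in part. Entry requires ECOG 0 or 1 and a life expectancy of at least 12 weeks, and the discontinuation MRI keeps some early failures in. The term disease assessment is not defined. Section 5.2.6.3 lists examination and performance status beside MRI, so some subjects too ill to scan might qualify. Subjects removed while alive, or for unrelated withdrawal, still raise ORR but need not raise OS. None of this retains a subject who dies before any assessment.

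*The SAP can settle it.* Section 7.1 leaves endpoint details to the SAP, and no passage says specifically that OS will be run in this set. But the population and its role are already fixed without exemption, so this is a rule as stated and not one left open.

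**Conclusion.** The point holds for OS and ORR in the secondary efficacy population. Both are biased in the drug's favour, and the rule conflicts with Appendix 4. The primary ITT analysis is not touched.

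The size rests on an assumed d. For ORR the relative inflation is 2% to 11% over d = 2% to 10%. For 6-month OS it is about 3 percentage points at d = 5% and 6 at d = 10%, and at most about 8 at d = 12.8%. The OS figures further assume exponential survival with a 7-month median and that all those removed are early deaths. Any additional effect on PFS or PFS-6 is conditional on how unscanned deaths are treated. It should be fixed, but it does not undermine the headline result.

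**What to change.** Amend Section 7.2 along these lines: *the evaluable population comprises every treated subject who either has one or more disease assessments after baseline, or dies or meets the clinical-progression criteria of Appendix 4 before the first such assessment.* Count the added subjects as non-responders in ORR. Report OS in the ITT and safety populations only.

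For PFS this is not enough. Also amend the Section 7.3.2.1 sentence that censors unscanned subjects at first dose, so that it excepts deaths and Appendix 4 progression. Those subjects then count as events on the date of death or clinical progression, in line with the any-cause-death wording of the PFS definition.

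The cost is two short text changes, carried into the SAP and programming. No new data are needed, because survival status and treatment discontinuation are already recorded. Doses, visits and sample size do not change. The only downside is slightly less favourable evaluable-population figures.

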## 7.3 Endpoints

### 7.3.1 Primary Endpoint

The primary objective of this study is to evaluate the PFS-6 in adult subjects with a first recurrence of GBM who are treated with MEDI-575.

The PFS-6 rate will be summarized and its 2-sided 90% CI will be calculated based on the Kaplan-Meier method ([Kaplan and Meier, 1958](#)).

### 7.3.2 Secondary Endpoints

The secondary objectives of this study are to evaluate other antitumor activities of MEDI-575; describe the safety and tolerability of MEDI-575; and evaluate the expression of PDGFR $\alpha$  in the tumor cells in archival tumor samples in this subject population. Endpoints related to these objectives are described below.

#### 7.3.2.1 Secondary Endpoints of Antitumor Activity of MEDI-575

Assessments of other antitumor activities include ORR, TTR, DR, TTP, PFS, and OS. *The Updated Response Assessment Criteria of High Grade Gliomas - Neuro-Oncology Working Group* ([Wen et al, 2010](#)) will be used to determine tumor response.

- Objective response rate is defined as the proportion of subjects with confirmed CR or confirmed PR according to the *Updated Response Assessment Criteria of High*

*Grade Gliomas- Neuro-Oncology Working Group (Wen et al, 2010)*. Confirmed responses are those that persist on repeat imaging studies at least 4 weeks after the initial documentation of response. The 2-sided 90% and 95% CIs of ORR will be estimated using the exact probability method.

- Time to response will be measured from the start of MEDI-575 administration to the first documentation of response (CR or PR) and will only be assessed in subjects who have achieved objective response.
- Duration of response will be defined as the duration from the first documentation of objective response to the first documented disease progression. Duration of response will be censored on the date of last tumor assessment documenting absence of disease progression for subjects who have no documented progression prior to data cutoff, dropout, or the initiation of alternate anticancer treatment. Duration of response will only be evaluated for the subgroup of subjects with an objective response and will be assessed using the Kaplan-Meier method.
- Time to progression will be measured from the start of treatment with MEDI-575 until the documentation of disease progression. Time to progression will be censored on the date of last tumor assessment documenting absence of tumor progression for subjects who have no documented progression prior to data cutoff, dropout, or the initiation of alternate anticancer treatment. Subjects having no tumor assessments after the start of treatment with MEDI-575 will have TTP censored on the first date of treatment with MEDI-575. Time to progression will be evaluated using the Kaplan-Meier method.
- Progression-free survival will be measured from the start of treatment with MEDI-575 until the documentation of disease progression or death due to any cause, whichever occurs first. Progression-free survival will be censored on the date of last tumor assessment documenting absence of tumor progression for subjects who have no documented progression and are still alive prior to data cutoff, dropout, or the initiation of alternate anticancer treatment. Subjects having no tumor assessments after the start of treatment with MEDI-575 will have PFS censored on the first date of treatment with MEDI-575. Progression-free survival will be evaluated using the Kaplan-Meier method.
- Overall survival will be determined as the time from the start of treatment with MEDI-575 until death. For subjects who are alive at the end of study or lost to follow-up, OS will be censored on the last date when subjects are known to be alive. Overall survival will be evaluated using the Kaplan-Meier method.

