### **3.4 Rationale for Study Design, Doses, and Control Groups**

This is a multicenter, open-label, single arm, single agent study of MEDI-575 to determine the safety and antitumor efficacy of MEDI-575 in adult subjects with first recurrence of GBM. Progression free survival at 6 months (PFS-6) will be used to determine efficacy, and provides a direct measure of the effect of MEDI-575 on antitumor activity. Progression free survival or PFS-6 may correlate with OS, and prolongation of PFS may in itself be a measure of clinical benefit. Unlike OS, measurement of PFS is not confounded by subsequent therapies. Overall survival and ORR will be secondary endpoints. Response and progression will be measured using proposed criteria developed by the Response Assessment in Neuro-Oncology (RANO) Working Group (see [Appendix 4](#) and [Appendix 5](#)), which will be assessed by an independent radiographic analysis.

The choice of a single-arm trial is appropriate given this patient population and the goals of the study. MEDI-575 has not yet been evaluated in GBM. Patients with recurrent GBM have no curative therapies, and there is still a need for additional therapies for this population. A PFS-6 of 15-20% is generally accepted as demonstration of clinical activity in patients with first recurrence of GBM ([Ballman et al, 2007](#); [Prados, 2006](#)). In the absence of therapy, all patients who have a recurrence will continue to progress rapidly. A randomized trial would require comparison to another agent, or addition to another agent, and would require a large number of patients from a very limited pool. In this patient population with very limited therapeutic options and no firmly established standard of care, a single-arm trial is an acceptable design to evaluate the single-agent activity.

The Phase 2 dose (25 mg/kg every 21 days) is based on the ongoing Phase 1 first time in human study (MI-CP187), which evaluates the safety, tolerability, and antitumor activity of MEDI-575 in advanced solid tumors refractory to standard therapy. In MI-CP187, a standard

3+3 dose-escalation study, MEDI-575 was evaluated at doses up to 15 mg/kg once every 7 days and 25 and 35 mg/kg every 21 days. No DLTs were identified at any doses, demonstrating that MEDI-575 appears to be tolerable. The Phase 2 dose was chosen based on PK/pharmacodynamic modeling using preclinical pharmacology models, as well as analysis in the Phase 1 study.

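### Duration of response as written censors a responder who dies without documented progression, while Appendix 4 can be read to make the same death a progression event

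*Protocol*

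**What the plan says.** Protocol Section 7.3.2.1 defines the DR event: "Duration of response will be defined as the duration from the first documentation of objective response to the first documented disease progression". Its censoring rule is: "Duration of response will be censored on the date of last tumor assessment documenting absence of disease progression for subjects who have no documented progression" before data cutoff, dropout or other anticancer treatment. DR is restricted to responders and "will be assessed using the Kaplan-Meier method".

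TTP in the same section has the same structure: "Time to progression will be measured from the start of treatment with MEDI-575 until the documentation of disease progression", with matching censoring wording.

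PFS, also in Section 7.3.2.1, treats death differently. Its event runs "until the documentation of disease progression or death due to any cause, whichever occurs first", and censoring is limited to subjects "who have no documented progression and are still alive prior to data cutoff, dropout, or the initiation of alternate anticancer treatment".

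Section 3.4 says which criteria decide progression: "Response and progression will be measured using proposed criteria developed by the Response Assessment in Neuro-Oncology (RANO) Working Group", pointing to Appendices 4 and 5. Section 5.3.7 points to the same appendices. Among the items that define progression, Appendix 4 includes "failure to return for evaluation as a result of death or deteriorating condition".

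**The concern.** The DR definition has neither of the two phrases that bring death into PFS. An analyst who follows Section 7.3.2.1 to the letter censors a responder who dies between scans at the last clear scan. An analyst who starts from Appendix 4 can call the same death progression and count it as an event. Both are following the protocol, and they report different DR results.

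This is more than detail left for a later plan, because the protocol itself states both the event and the censoring rule. Death ends a response and is unlikely to be independent of losing it. A curve that censors deaths therefore describes something more favourable than the time a responder stays alive and free of progression.

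Responders may be few. At the response rate of at most 15% that Section 1.1 cites for single-agent irinotecan, 55 subjects would give 55 × 0.15 = 8.25, or about 8 responders, so one or two deaths could move the median.

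**Working it through.** The protocol states no DR figure, so there is none to reproduce. The check has two parts: how the rules treat one death, and how far apart the readings can be.

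**1. One death under each rule.** Scans on treatment are every 6 weeks from Cycle 3 (Section 5.2.4), that is at about weeks 6, 12, 18 and 24. Take a hypothetical responder with response first documented at week 6, a clear scan at week 18, and death before the week 24 scan.

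| Rule | Treatment of this death |
|---|---|
| PFS, Section 7.3.2.1 | Event, at death |
| DR, Section 7.3.2.1 read literally | Censored at week 18, so 18 - 6 = 12 weeks |
| DR, if the Appendix 4 item counts as documented progression | Event |
| TTP, Section 7.3.2.1 | Same two readings as DR |

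**2. Size, continuous observation.** The assumptions are not from the protocol: constant hazards, and a share f of DR endings that are deaths without documented progression, from 5% to 30%. Let λ be the total hazard, so the progression hazard is (1-f)λ.

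- Median with deaths censored: ln 2 / [(1-f)λ]
- Median with deaths counted: ln 2 / λ
- Ratio: 1/(1-f)

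| f | 1/(1-f) |
|---|---|
| 5% | 1/0.95 = 1.05 |
| 10% | 1/0.90 = 1.11 |
| 20% | 1/0.80 = 1.25 |
| 30% | 1/0.70 = 1.43 |

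**3. Size, 6-weekly scans.** Assume further a true median to progression or death of 26 weeks, with progression found at the next scan. The chance that a response ends within one interval is q = 1 - 2^(-6/26) = 0.148. With deaths censored at the previous scan, the Kaplan-Meier step at each scan is h = (1-f)q / (1 - fq), and the curve after k scans is (1-h)^k. With deaths counted, the curve stays above one half until week 30, where it falls to (1-q)^5 = 0.449.

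| f | h | Censored: week 30 | Censored: week 36 | Median, censored | Median, counted |
|---|---|---|---|---|---|
| 10% | 0.135 | 0.484 | 0.419 | 30 weeks | 30 weeks |
| 20% | 0.122 | 0.522 | 0.459 | 36 weeks | 30 weeks |
| 30% | 0.108 | 0.503 at week 36, so not yet below half | 0.448 at week 42 | 42 weeks | 30 weeks |

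(For f = 30% the two curve columns show weeks 36 and 42.) The median moves in 6-week steps, so a small f may show no shift and a larger f shows a whole step. The 30% row lies close to a step: the censored curve is only 0.003 above one half at week 36, so a finite simulation can return 36 weeks. One of 8,000 responders gave 36 against 29 weeks.

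**The case against.** DR and TTP form a progression-based pair with almost identical wording, while PFS is defined to include death. Endpoints may count different events. A reader might infer that DR contradicts the PFS rule, but the protocol does not support that. It is inconsistent handling of death, and by the same argument TTP would contradict PFS too. This part of the objection stands.

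Appendix 4 may already settle the case. If its failure-to-return item makes a death documented progression, the DR censoring rule never reaches that subject and there is no inflation. Nothing in Section 7.3.2.1 restricts documentation to imaging. That reading is available but not compelled: the DR rule censors on the date of a tumor assessment, and Section 5.3.7 assigns progression to blinded central imaging review, which has nothing to read when there is no scan. Nor can the inflation and the Appendix 4 event both apply to the same death; they belong to alternative readings. The defect is that the text leaves both open.

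A reader might also infer a definite overstatement, for instance of 10% to 30%. The protocol gives no basis for one. Appendix 4 already counts clear clinical deterioration as progression, and scans continue every 3 months after treatment stops for reasons other than progression or new therapy (Section 5.2.6.3), so deaths without documented progression may be uncommon. Under constant, independent hazards the ratio compares two estimands, progression alone and progression or death. It does not measure bias in estimating the first. It would also be inexact to say that a dead responder is counted as still responding: nothing is observed after the last clear scan.

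**Conclusion.** The point holds as a defect of definition. The DR censoring rule in Section 7.3.2.1 and the progression criteria in Appendix 4 can give opposite answers for the same death, and the protocol does not say which applies. Under the literal reading, the estimate is generally longer than time to progression or death once a responder dies without documented progression.

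How much longer depends on an unknown f. The factor of 1.05 to 1.43 rests on an assumed f of 5% to 30% and constant hazards. With 6-weekly scans the median may not move at all at small f, and there is no difference if no such death occurs.

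The consequence is minor. DR is a secondary, descriptive endpoint in responders only. The trial's success rule rests on the lower confidence bound for PFS-6 (Section 7.5), so the primary analysis, alpha and power are untouched.

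**What to change.** In Section 7.3.2.1, define DR as the time from first documented response to documented progression or death from any cause, whichever is earlier, and censor only responders who are alive without progression. State in the same section whether the Appendix 4 failure-to-return item counts as documented progression for DR and for TTP. If leaving death out of DR is deliberate, say so and explain how that fits with Appendix 4.

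The cost is a few words. No new data are needed, because survival status is already collected in every subject (Section 5.2.6.3). The downside is that the reported DR may be slightly shorter.
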